#### **17.4.1.6. History of COVID-19**

##### **17.4.1.6.1. ICD-10-CM Codes**

- U07.1 COVID-19, virus identified
- B97.29 Other coronavirus as the cause of diseases classified elsewhere
- J12.82 Pneumonia due to coronavirus disease 2019
- Z86.16 Personal history of COVID-19

#### **17.4.1.7. Immunocompromised Status**

##### **17.4.1.7.1. ICD-10-CM Codes**

- D80.0 Hereditary hypogammaglobulinemia
- D80.1 Nonfamilial hypogammaglobulinemia
- D80.2 Selective deficiency of immunoglobulin A [IgA]
- D80.3 Selective deficiency of immunoglobulin G [IgG] subclasses
- D80.4 Selective deficiency of immunoglobulin M [IgM]
- D80.5 Immunodeficiency with increased immunoglobulin M [IgM]
- D80.6 Antibody deficiency with near-normal immunoglobulins or with hyperimmunoglobulinemia

- D80.7 Transient hypogammaglobulinemia of infancy
- D80.8 Other immunodeficiencies with predominantly antibody defects
- D80.9 Immunodeficiency with predominantly antibody defects, unspecified
- D81.0 Severe combined immunodeficiency [SCID] with reticular dysgenesis
- D81.1 Severe combined immunodeficiency [SCID] with low T- and B-cell numbers
- D81.2 Severe combined immunodeficiency [SCID] with low or normal B-cell numbers
- D81.30 Adenosine deaminase deficiency, unspecified
- D81.31 Severe combined immunodeficiency due to adenosine deaminase deficiency
- D81.32 Adenosine deaminase 2 deficiency
- D81.39 Other adenosine deaminase deficiency
- D81.4 Nezelof's syndrome
- D81.5 Purine nucleoside phosphorylase [PNP] deficiency
- D81.6 Major histocompatibility complex class I deficiency
- D81.7 Major histocompatibility complex class II deficiency
- D81.8 Other combined immunodeficiencies
- D81.81 Biotin-dependent carboxylase deficiency
- D81.810 Biotinidase deficiency
- D81.818 Other biotin-dependent carboxylase deficiency
- D81.819 Biotin-dependent carboxylase deficiency, unspecified
- D81.89 Other combined immunodeficiencies
- D81.9 Combined immunodeficiency, unspecified
- D82.0 Wiskott-Aldrich syndrome
- D82.1 Di George's syndrome

D82.2	Immunodeficiency with short-limbed stature
D82.3	Immunodeficiency following hereditary defective response to Epstein-Barr virus
D82.4	Hyperimmunoglobulin E [IgE] syndrome
D82.8	Immunodeficiency associated with other specified major defects
D82.9	Immunodeficiency associated with major defect, unspecified
D83	Common variable immunodeficiency
D83.0	Common variable immunodeficiency with predominant abnormalities of B-cell numbers and function
D83.1	Common variable immunodeficiency with predominant immunoregulatory T-cell disorders
D83.2	Common variable immunodeficiency with autoantibodies to B- or T-cells
D83.8	Other common variable immunodeficiencies
D83.9	Common variable immunodeficiency, unspecified
D84.0	Lymphocyte function antigen-1 [LFA-1] defect
D84.1	Defects in the complement system
D84.8	Other specified immunodeficiencies
D84.9	Immunodeficiency, unspecified
B20	Human immunodeficiency virus [HIV] disease
Z21	Asymptomatic human immunodeficiency virus [HIV] infection status
O98.7	Human immunodeficiency virus [HIV] disease complicating pregnancy, childbirth and the puerperium
B97.35	Human immunodeficiency virus, type 2 [HIV 2] as the cause of diseases classified elsewhere
Z94.0	Kidney transplant status
Z94.1	Heart transplant status

Z94.2	Lung transplant status
Z94.3	Heart and lungs transplant status
Z94.4	Liver transplant status
Z94.5	Skin transplant status
Z94.6	Bone transplant status
Z94.7	Corneal transplant status
Z94.81	Bone marrow transplant status
Z94.82	Intestine transplant status
Z94.83	Pancreas transplant status
Z94.84	Stem cells transplant status
Z94.89	Other transplanted organ and tissue status
Z94.9	Transplanted organ and tissue status, unspecified

#### **17.4.1.7.2. CPT Codes**

33935	Heart-lung transplant with recipient cardiectomy-pneumonectomy
33945	Heart transplant, with or without recipient cardiectomy
80158	Cyclosporine
80197	Tacrolimus
80195	Sirolimus
80180	Mycophenolate (mycophenolic acid)

#### **17.4.1.7.3. HCPCS Codes**

J0485	Injection, belatacept, 1 mg
J7500	Azathioprine, oral, 50 mg
J7501	Azathioprine, parenteral, 100 mg

---

 CPT copyright 2024 American Medical Association. All rights reserved.

J7502	Cyclosporine, oral, 100 mg
J7503	Tacrolimus, extended release, (Envarsus XR), oral, 0.25 mg
J7504	Lymphocyte immune globulin, antithymocyte globulin, equine, parenteral, 250 mg
J7505	Muromonab-CD3, parenteral, 5 mg
J7507	Tacrolimus, immediate release, oral, 1 mg
J7508	Tacrolimus, extended release, (Astagraf XL), oral, 0.1 mg
J7509	Methylprednisolone oral, per 4 mg
J7510	Prednisolone oral, per 5 mg
J7511	Lymphocyte immune globulin, antithymocyte globulin, rabbit, parenteral, 25 mg
J7512	Prednisone, immediate release or delayed release, oral, 1 mg
J7513	Daclizumab, parenteral, 25 mg
J7515	Cyclosporine, oral, 25 mg
J7516	Cyclosporin, parenteral, 250 mg
J7517	Mycophenolate mofetil, oral, 250 mg
J7518	Mycophenolic acid, oral, 180 mg
J7519	Injection, mycophenolate mofetil, 10 mg
J7520	Sirolimus, oral, 1 mg
J7525	Tacrolimus, parenteral, 5 mg
J7527	Everolimus, oral, 0.25 mg
J7599	Immunosuppressive drug, not otherwise classified
J8530	Cyclophosphamide; oral, 25 mg
J8610	Methotrexate; oral, 2.5 mg

090177e1a5be86fe\Approved\Approved On: 19-Mar-2026 15:57 (GMT)

#### 17.4.1.7.4. NDC Codes

NDC codes corresponding to the above immunosuppressant medications will be utilized where applicable.

#### 17.4.1.8. Kidney Disorders

##### 17.4.1.8.1. ICD-10-CM Codes

N00.0	Acute nephritic syndrome with minor glomerular abnormality
N00.1	Acute nephritic syndrome with focal and segmental glomerular lesions
N00.2	Acute nephritic syndrome with diffuse membranous glomerulonephritis
N00.3	Acute nephritic syndrome with diffuse mesangial proliferative glomerulonephritis
N00.4	Acute nephritic syndrome with diffuse endocapillary proliferative glomerulonephritis
N00.5	Acute nephritic syndrome with diffuse mesangiocapillary glomerulonephritis
N00.6	Acute nephritic syndrome with dense deposit disease
N00.7	Acute nephritic syndrome with diffuse crescentic glomerulonephritis
N00.8	Acute nephritic syndrome with other morphologic changes
N00.9	Acute nephritic syndrome with unspecified morphologic changes
N01.0	Rapidly progressive nephritic syndrome with minor glomerular abnormality
N01.1	Rapidly progressive nephritic syndrome with focal and segmental glomerular lesions
N01.2	Rapidly progressive nephritic syndrome with diffuse membranous glomerulonephritis
N01.3	Rapidly progressive nephritic syndrome with diffuse mesangial proliferative glomerulonephritis
N01.4	Rapidly progressive nephritic syndrome with diffuse endocapillary proliferative glomerulonephritis

090177e1a5be86fe\Approved\Approved On: 19-Mar-2026 15:57 (GMT)

- N01.5 Rapidly progressive nephritic syndrome with diffuse mesangiocapillary glomerulonephritis
- N01.6 Rapidly progressive nephritic syndrome with dense deposit disease
- N01.7 Rapidly progressive nephritic syndrome with diffuse crescentic glomerulonephritis
- N01.8 Rapidly progressive nephritic syndrome with other morphologic changes
- N01.9 Rapidly progressive nephritic syndrome with unspecified morphologic changes
- N02.0 Recurrent and persistent hematuria with minor glomerular abnormality
- N02.1 Recurrent and persistent hematuria with focal and segmental glomerular lesions
- N02.2 Recurrent and persistent hematuria with diffuse membranous glomerulonephritis
- N02.3 Recurrent and persistent hematuria with diffuse mesangial proliferative glomerulonephritis
- N02.4 Recurrent and persistent hematuria with diffuse endocapillary proliferative glomerulonephritis
- N02.5 Recurrent and persistent hematuria with diffuse mesangiocapillary glomerulonephritis
- N02.6 Recurrent and persistent hematuria with dense deposit disease
- N02.7 Recurrent and persistent hematuria with diffuse crescentic glomerulonephritis
- N02.8 Recurrent and persistent hematuria with other morphologic changes
- N02.9 Recurrent and persistent hematuria with unspecified morphologic changes
- N03.0 Chronic nephritic syndrome with minor glomerular abnormality
- N03.1 Chronic nephritic syndrome with focal and segmental glomerular lesions
- N03.2 Chronic nephritic syndrome with diffuse membranous glomerulonephritis

- N03.3 Chronic nephritic syndrome with diffuse mesangial proliferative glomerulonephritis
- N03.4 Chronic nephritic syndrome with diffuse endocapillary proliferative glomerulonephritis
- N03.5 Chronic nephritic syndrome with diffuse mesangiocapillary glomerulonephritis
- N03.6 Chronic nephritic syndrome with dense deposit disease
- N03.7 Chronic nephritic syndrome with diffuse crescentic glomerulonephritis
- N03.8 Chronic nephritic syndrome with other morphologic changes
- N03.9 Chronic nephritic syndrome with unspecified morphologic changes
- N04.0 Nephrotic syndrome with minor glomerular abnormality
- N04.1 Nephrotic syndrome with focal and segmental glomerular lesions
- N04.2 Nephrotic syndrome with diffuse membranous glomerulonephritis
- N04.3 Nephrotic syndrome with diffuse mesangial proliferative glomerulonephritis
- N04.4 Nephrotic syndrome with diffuse endocapillary proliferative glomerulonephritis
- N04.5 Nephrotic syndrome with diffuse mesangiocapillary glomerulonephritis
- N04.6 Nephrotic syndrome with dense deposit disease
- N04.7 Nephrotic syndrome with diffuse crescentic glomerulonephritis
- N04.8 Nephrotic syndrome with other morphologic changes
- N04.9 Nephrotic syndrome with unspecified morphologic changes
- N05.0 Unspecified nephritic syndrome with minor glomerular abnormality
- N05.1 Unspecified nephritic syndrome with focal and segmental glomerular lesions
- N05.2 Unspecified nephritic syndrome with diffuse membranous glomerulonephritis

090177e1a5be86fe\Approved\Approved On: 19-Mar-2026 15:57 (GMT)

- N05.3 Unspecified nephritic syndrome with diffuse mesangial proliferative glomerulonephritis
- N05.4 Unspecified nephritic syndrome with diffuse endocapillary proliferative glomerulonephritis
- N05.5 Unspecified nephritic syndrome with diffuse mesangiocapillary glomerulonephritis
- N05.6 Unspecified nephritic syndrome with dense deposit disease
- N05.7 Unspecified nephritic syndrome with diffuse crescentic glomerulonephritis
- N05.8 Unspecified nephritic syndrome with other morphologic changes
- N05.9 Unspecified nephritic syndrome with unspecified morphologic changes
- N06.0 Isolated proteinuria with minor glomerular abnormality
- N06.1 Isolated proteinuria with focal and segmental glomerular lesions
- N06.2 Isolated proteinuria with diffuse membranous glomerulonephritis
- N06.3 Isolated proteinuria with diffuse mesangial proliferative glomerulonephritis
- N06.4 Isolated proteinuria with diffuse endocapillary proliferative glomerulonephritis
- N06.5 Isolated proteinuria with diffuse mesangiocapillary glomerulonephritis
- N06.6 Isolated proteinuria with dense deposit disease
- N06.7 Isolated proteinuria with diffuse crescentic glomerulonephritis
- N06.8 Isolated proteinuria with other morphologic lesion
- N06.9 Isolated proteinuria with unspecified morphologic lesion
- N07.0 Hereditary nephropathy, not elsewhere classified with minor glomerular abnormality
- N07.1 Hereditary nephropathy, not elsewhere classified with focal and segmental glomerular lesions

090177e1a5be86fe\Approved\Approved On: 19-Mar-2026 15:57 (GMT)

- N07.2 Hereditary nephropathy, not elsewhere classified with diffuse membranous glomerulonephritis
- N07.3 Hereditary nephropathy, not elsewhere classified with diffuse mesangial proliferative glomerulonephritis
- N07.4 Hereditary nephropathy, not elsewhere classified with diffuse endocapillary proliferative glomerulonephritis
- N07.5 Hereditary nephropathy, not elsewhere classified with diffuse mesangiocapillary glomerulonephritis
- N07.6 Hereditary nephropathy, not elsewhere classified with dense deposit disease
- N07.7 Hereditary nephropathy, not elsewhere classified with diffuse crescentic glomerulonephritis
- N07.8 Hereditary nephropathy, not elsewhere classified with other morphologic lesions
- N07.9 Hereditary nephropathy, not elsewhere classified with unspecified morphologic lesions
- N08 Glomerular disorders in diseases classified elsewhere
- N10 Acute pyelonephritis
- N11.0 Nonobstructive reflux-associated chronic pyelonephritis
- N11.1 Chronic obstructive pyelonephritis
- N11.8 Other chronic tubulo-interstitial nephritis
- N11.9 Chronic tubulo-interstitial nephritis, unspecified
- N12 Tubulo-interstitial nephritis, not specified as acute or chronic
- N13.0 Hydronephrosis with ureteropelvic junction obstruction
- N13.1 Hydronephrosis with ureteral stricture, not elsewhere classified
- N13.2 Hydronephrosis with renal and ureteral calculous obstruction
- N13.30 Unspecified hydronephrosis
- N13.39 Other hydronephrosis

090177e1a5be86fe\Approved\Approved On: 19-Mar-2026 15:57 (GMT)

- N13.4 Hydroureter
- N13.5 Crossing vessel and stricture of ureter without hydronephrosis
- N13.6 Pyonephrosis
- N13.70 Vesicoureteral-reflux, unspecified
- N13.71 Vesicoureteral-reflux without reflux nephropathy
- N13.721 Vesicoureteral-reflux with reflux nephropathy without hydroureter, unilateral
- N13.722 Vesicoureteral-reflux with reflux nephropathy without hydroureter, bilateral
- N13.729 Vesicoureteral-reflux with reflux nephropathy without hydroureter, unspecified
- N13.731 Vesicoureteral-reflux with reflux nephropathy with hydroureter, unilateral
- N13.732 Vesicoureteral-reflux with reflux nephropathy with hydroureter, bilateral
- N13.739 Vesicoureteral-reflux with reflux nephropathy with hydroureter, unspecified
- N13.8 Other obstructive and reflux uropathy
- N13.9 Obstructive and reflux uropathy, unspecified
- N14.0 Analgesic nephropathy
- N14.1 Nephropathy induced by other drugs, medicaments and biological substances
- N14.2 Nephropathy induced by unspecified drug, medicament or biological substance
- N14.3 Nephropathy induced by heavy metals
- N14.4 Toxic nephropathy, not elsewhere classified
- N15.0 Balkan nephropathy
- N15.1 Renal and perinephric abscess

090177e1a5be86fe\Approved\Approved On: 19-Mar-2026 15:57 (GMT)

- N15.8 Other specified renal tubulo-interstitial diseases
- N15.9 Renal tubulo-interstitial disease, unspecified
- N16 Renal tubulo-interstitial disorders in diseases classified elsewhere
- N17.0 Acute kidney failure with tubular necrosis
- N17.1 Acute kidney failure with acute cortical necrosis
- N17.2 Acute kidney failure with medullary necrosis
- N17.8 Other acute kidney failure
- N17.9 Acute kidney failure, unspecified
- N18.1 Chronic kidney disease, stage 1
- N18.2 Chronic kidney disease, stage 2 (mild)
- N18.3 Chronic kidney disease, stage 3 (moderate)
- N18.4 Chronic kidney disease, stage 4 (severe)
- N18.5 Chronic kidney disease, stage 5
- N18.6 End stage renal disease
- N18.9 Chronic kidney disease, unspecified
- N19 Unspecified kidney failure
- N20.0 Calculus of kidney
- N20.1 Calculus of ureter
- N20.2 Calculus of kidney with calculus of ureter
- N20.9 Urinary calculus, unspecified
- N23 Unspecified renal colic
- N25.0 Renal osteodystrophy
- N25.1 Nephrogenic diabetes insipidus
- N25.81 Secondary hyperparathyroidism of renal origin

090177e1a5be86fe\Approved\Approved On: 19-Mar-2026 15:57 (GMT)

- N25.89 Other disorders resulting from impaired renal tubular function
- N25.9 Disorder resulting from impaired renal tubular function, unspecified
- N26 Unspecified contracted kidney
- N26.1 Atrophy of kidney (terminal)
- N26.2 Page kidney
- N26.9 Renal sclerosis, unspecified
- N27.0 Small kidney, unilateral
- N27.1 Small kidney, bilateral
- N27.9 Small kidney, unspecified
- N28.0 Ischemia and infarction of kidney
- N28.1 Cyst of kidney, acquired
- N28.81 Hypertrophy of kidney
- N28.82 Megaloureter
- N28.83 Nephroptosis
- N28.84 Pyelitis cystica
- N28.85 Pyeloureteritis cystica
- N28.86 Ureteritis cystica
- N28.89 Other specified disorders of kidney and ureter
- N28.9 Disorder of kidney and ureter, unspecified
- N29 Other disorders of kidney and ureter in diseases classified elsewhere

090177e1a5be86fe\Approved\Approved On: 19-Mar-2026 15:57 (GMT)

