#### 9.1.1. SCRI

Phase 1 will monitor the incidence rate of pre-specified safety events of interest in a general population of individuals who receive the COMIRNATY 2023-2024 Formula using an SCRI study design that tracks post-vaccination risk intervals and control (reference) periods for each vaccinated individual. Monitoring will be conducted during a pre-specified risk period immediately following vaccination, and the observed rate of events during this risk period will be compared to that of a control period temporally removed from the vaccination event. As depicted in [Figure 1](#), only individuals who receive the COMIRNATY 2023-2024 Formula will be included in the SCRI study ([Baker et al., 2015](#)). Within each individual, outcomes occurring during the risk interval will be compared with those occurring during the control period, in order to determine whether these outcomes occur more frequently immediately after vaccination as compared with a reference period. A washout period may be inserted between the risk interval and the control period to ensure that events relating to the vaccine are not incorrectly attributed to the control period. To ensure that observed outcomes are truly incident, a period free from the outcome of interest (clean period) may be required prior to vaccination.

090177e1a5be86fe\Approved\Approved On: 19-Mar-2026 15:57 (GMT)

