### 9.2.1. SCRI

#### 9.2.1.1. Inclusion Criteria

Patients must meet all of the following inclusion criteria to be eligible for inclusion in Phase 1 of the study:

1. Receive at least one dose of the COMIRNATY 2023-2024 Formula from the date of the COMIRNATY 2023-2024 product launch through 31 March 2024.
2. Age  $\geq$  6 months when receiving their first recorded dose of the COMIRNATY 2023-2024 Formula.
3. Have continuous medical and pharmacy insurance coverage in the 365 days prior to their vaccination date (as defined in [Section 9.2.3](#)), or since birth if the vaccination occurred at  $<$  1 year of age.
4. Experience a safety outcome of interest during a risk interval or control period (on or after vaccination, as defined in [Section 9.3.2](#)).
5. Do not experience the safety outcome of interest during the clean period (prior to vaccination, as defined in [Section 9.3.2](#)).

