#### **9.2.2.2. Exclusion Criteria**

Patients meeting any of the following criteria will not be included in Phase 2 of the study:

1. Are of unknown sex.
2. Have a missing month and year of birth.
3. Have received a COVID-19 vaccine in the 270 days prior to cohort entry date (as defined in Section 9.2.3).
4. Have received both the COMIRNATY 2023-2024 Formula and a COVID-19 vaccine other than the COMIRNATY 2023-2024 Formula on the cohort entry date (defined in Section 9.2.3).

In both phases of the study, when creating the analytic population for each specific safety outcome of interest, individuals will be excluded if they experienced that safety outcome during the portion of the baseline period designated as the clean period ([Section 9.2.4](#)).

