### 9.3.2. Outcomes

In both the SCRI and cohort studies, the pre-specified safety outcomes of interest will include the following:

- ADEM
- Anaphylaxis
- Bell's palsy
- CVST
- Convulsions/seizures (non-febrile)
- Encephalomyelitis
- Glomerulonephritis
- Guillain-Barré syndrome
- Herpes zoster
- Immune-mediated myositis
- Immune thrombocytopenia
- Kawasaki disease
- Multi inflammatory syndrome (in children and adults)
- MS
- MI
- Myocarditis/pericarditis
- PE
- Stroke, hemorrhagic
- Stroke, ischemic
- Transverse myelitis

In addition, in Phase 2 of the study, the following pregnancy outcomes will be assessed in pregnant women or their infants, if sample size permits:

- Spontaneous abortion
- Stillbirth
- Preterm birth
- Major congenital malformations
- Small for gestational age

Code lists for the safety outcomes of interest are provided in [Annex 2 \(Appendix III\)](#). Corresponding site of care requirements are listed in Table 2. When possible, outcomes will be defined using a validated claims-based algorithm with high performance ([CBER, 2021](#)).

If a safety signal is detected in the interim report, then medical records will be retrieved for a subset of participants to confirm the presence of that study outcome. A safety signal that requires confirmation through medical record review will be defined as a rate ratio of > 3.0 and a corresponding P value of < 0.01 in the primary analysis of the SCRI design (details in [Section 9.7.1.1](#)). Additionally, medical record review may be conducted for analyses beyond the primary SCRI analysis if a safety signal (defined as a rate ratio of > 3.0 and a corresponding P value of < 0.01) is detected in the interim or final report. Medical records may also be retrieved for AESIs with estimates approaching the pre-specified safety signal threshold.

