### 17.3. Appendix III – Safety Outcomes of Interest

All codes are ICD-10 diagnosis codes; all outcomes will be defined based on the presence of a single code unless otherwise specified. In order to qualify as an outcome, the outcome-specific codes must be identified during emergency department visits, inpatient hospitalizations, or outpatient visits, as detailed in [Table 2](#). Outpatient visits are defined through physician evaluation and management codes ([Section 17.2.3](#)).

\* Outcome codes marked with an asterisk are based on COVID-19 vaccine studies conducted as part of the FDA’s CBER BEST system.

- Acute disseminated encephalomyelitis (ADEM)\*
  - G04.00 – Acute disseminated encephalitis and encephalomyelitis, unspecified
- Anaphylaxis\*
  - T80.52XA – Anaphylactic reaction due to vaccination, initial encounter
  - T78.2XXA – Anaphylactic shock, unspecified, initial encounter
- Bell's palsy\*
  - G51.0 – Bell’s palsy
  - G51.8 – Other disorders of facial nerve
  - G51.9 – Disorder of facial nerve, unspecified
- Cerebral venous sinus thrombosis (CVST)
  - I67.6 – Nonpyogenic thrombosis of intracranial venous system
  - I63.6 – Cerebral infarction due to cerebral venous thrombosis, nonpyogenic
- Convulsions/seizures (non-febrile)
  - G40.001 – Localization-related (focal) (partial) idiopathic epilepsy and epileptic syndromes with seizures of localized onset, not intractable, with status epilepticus
  - G40.009 – Localization-related (focal) (partial) idiopathic epilepsy and epileptic syndromes with seizures of localized onset, not intractable, without status epilepticus
  - G40.011 – Localization-related (focal) (partial) idiopathic epilepsy and epileptic syndromes with seizures of localized onset, intractable, with status epilepticus
  - G40.019 – Localization-related (focal) (partial) idiopathic epilepsy and epileptic syndromes with seizures of localized onset, intractable, without status epilepticus
  - G40.101 – Localization-related (focal) (partial) symptomatic epilepsy and epileptic syndromes with simple partial seizures, not intractable, with status epilepticus

090177e1a5be86fe\Approved\Approved On: 19-Mar-2026 15:57 (GMT)

- G40.109 – Localization-related (focal) (partial) symptomatic epilepsy and epileptic syndromes with simple partial seizures, not intractable, without status epilepticus

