- G40.812 – Lennox-Gastaut syndrome, not intractable, without status epilepticus
- G40.813 – Lennox-Gastaut syndrome, intractable, with status epilepticus
- G40.814 – Lennox-Gastaut syndrome, intractable, without status epilepticus
- G40.821 – Epileptic spasms, not intractable, with status epilepticus
- G40.822 – Epileptic spasms, not intractable, without status epilepticus
- G40.823 – Epileptic spasms, intractable, with status epilepticus
- G40.824 – Epileptic spasms, intractable, without status epilepticus
- G40.89 – Other seizures
- G40.901 – Epilepsy, unspecified, not intractable, with status epilepticus
- G40.909 – Epilepsy, unspecified, not intractable, without status epilepticus
- G40.911 – Epilepsy, unspecified, intractable, with status epilepticus
- G40.919 – Epilepsy, unspecified, intractable, without status epilepticus
- G40.A01 – Absence epileptic syndrome, not intractable, with status epilepticus
- G40.A09 – Absence epileptic syndrome, not intractable, without status epilepticus
- G40.A11 – Absence epileptic syndrome, intractable, with status epilepticus
- G40.A19 – Absence epileptic syndrome, intractable, without status epilepticus
- G40.B01 – Juvenile myoclonic epilepsy, not intractable, with status epilepticus
- G40.B09 – Juvenile myoclonic epilepsy, not intractable, without status epilepticus
- G40.B11 – Juvenile myoclonic epilepsy, intractable, with status epilepticus
- G40.B19 – Juvenile myoclonic epilepsy, intractable, without status epilepticus
- R56.1 – Post traumatic seizures
- R56.9 – Unspecified convulsions

- Encephalomyelitis\*
  - G04.02 – Postimmunization acute disseminated encephalitis, myelitis, and encephalomyelitis
  - G04.00 – Acute disseminated encephalitis and encephalomyelitis, unspecified
  - G04.81 – Other encephalitis and encephalomyelitis
  - G04.90 – Encephalitis and encephalomyelitis
  - G05.3 – Encephalitis and encephalomyelitis in diseases classified elsewhere
- Glomerulonephritis
  - N06.A Isolated proteinuria with C3 glomerulonephritis
  - N06.7 Isolated proteinuria with diffuse crescentic glomerulonephritis
  - N06.5 Isolated proteinuria with diffuse mesangiocapillary glomerulonephritis
  - N06.4 Isolated proteinuria with diffuse endocapillary proliferative glomerulonephritis
  - N04.A Nephrotic syndrome with C3 glomerulonephritis
  - N04.2 Nephrotic syndrome with diffuse membranous glomerulonephritis
  - N04.7 Nephrotic syndrome with diffuse crescentic glomerulonephritis

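### The glomerulonephritis clean period screens only the 25 outcome codes, so glomerular disease coded before Day 0 under other N00-N08 codes can enter as incident

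*Protocol*

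**What the plan says.** Section 9.1.1 gives the purpose of the clean period: "To ensure that observed outcomes are truly incident, a period free from the outcome of interest (clean period) may be required prior to vaccination". SCRI inclusion criterion 5 (Section 9.2.1.1) reads "Do not experience the safety outcome of interest during the clean period". For both phases, Section 9.2.2.2 adds that "individuals will be excluded if they experienced that safety outcome during the portion of the baseline period designated as the clean period".

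The outcome itself is fixed by a code list. Section 9.3.2 states "Code lists for the safety outcomes of interest are provided in" Annex 2, Appendix III, and Section 17.3 says that "all outcomes will be defined based on the presence of a single code unless otherwise specified". Under glomerulonephritis that appendix lists codes which mostly name a histological form, for example "N04.2 Nephrotic syndrome with diffuse membranous glomerulonephritis". Table 2 sets the clean period at Days -365 to 0 and the risk interval at Days 1 to 42, with inpatient and outpatient claims both counting.

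No broader list for prevalent disease is given. Section 7 calls the document a combined protocol and SAP, and Annex 1 lists no standalone documents, so the rule is not deferred elsewhere. The kidney list in Section 17.4.1.8.1 covers N00.0 to N07.9 and N08, including "N04.9 Nephrotic syndrome with unspecified morphologic changes" and "N05.9 Unspecified nephritic syndrome with unspecified morphologic changes". It serves as a binary propensity score covariate and for the comorbidity subgroup, not for exclusion.

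**The concern.** Glomerular disease is often coded first as an unspecified syndrome and made specific later. The same lesion can also be coded under a different syndrome heading. A clean period built from the outcome codes alone sees neither case. A person under care for nephrotic syndrome (N04.9) in the prior year whose first membranous code (N04.2) comes after vaccination is counted as a new event, although the disease began before Day 0 and cannot have been caused by the vaccine.

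The stated aim of incident outcomes is then not secured for an event that Section 7 names among four drawn from VAERS reports. In the SCRI, recodings unrelated to vaccine timing dilute the rate ratio. That matters because mandatory medical record review under Section 9.3.2 needs a rate ratio above 3.0 with P below 0.01. In the cohort, follow-up of up to one year leaves much more time for a code to change than a 42-day window does.

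**Working it through.** The plan states no code count and no share of recoded cases, so there is no figure of its own to reproduce.

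**Code sets**

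- Outcome list (Section 17.3, glomerulonephritis): 25 distinct codes.
- Kidney list, N00-N08 block (Section 17.4.1.8.1): N00 to N07 each carry .0 to .9, plus N08, so 8 × 10 + 1 = 81.
- In both lists: 18. The other 25 − 18 = 7 outcome codes are the C3 '.A' codes (N00, N02-N07), which the kidney list lacks.
- In the kidney list but not the outcome list: 81 − 18 = **63**.
- Of the 63, those with glomerulonephritis in the label: N00.3-.4 (2), N01.2-.5 and .7 (5), N02.2-.5 (4), N03.3-.4 (2), N05.3-.4 (2), N06.2-.3 (2), N07.2-.5 and .7 (5), in total **22**.
- Also among the 63 are the unspecified nephritic and nephrotic codes N00.9, N01.9, N03.9, N04.9 and N05.9. All ten N01 codes are outside the outcome list.

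**Route into the analysis.** Take a person coded N03.3 (chronic nephritic syndrome, mesangial proliferative form) in the prior year. N03.3 is not an outcome code, so the clean period is passed. N04.3 (nephrotic syndrome, same lesion) is an outcome code, and one claim is enough. A first N04.3 claim on Day 20 counts as incident. N04.9 followed by N04.2 works the same way.

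**Dilution in the SCRI.** Let f be the share of all counted events that are recodings, split evenly over the two windows. Section 9.3.2.1 makes the windows equal in length. With true rate ratio RR,

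observed RR = [(1 − f)·RR/(1 + RR) + f/2] / [(1 − f)/(1 + RR) + f/2]

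| True RR | f | Numerator | Denominator | Observed |
|---|---|---|---|---|
| 2 | 0.10 | 0.600 + 0.050 = 0.650 | 0.300 + 0.050 = 0.350 | 1.86 |
| 2 | 0.50 | 0.333 + 0.250 = 0.583 | 0.167 + 0.250 = 0.417 | 1.40 |
| 3 | 0.10 | 0.675 + 0.050 = 0.725 | 0.225 + 0.050 = 0.275 | 2.64 |
| 3 | 0.50 | 0.375 + 0.250 = 0.625 | 0.125 + 0.250 = 0.375 | 1.67 |

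For the review threshold, a true RR of 3.5 with f = 0.10 gives (0.700 + 0.050)/(0.200 + 0.050) = 3.0, which no longer exceeds 3.0.

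The range for f is an assumption; the documents supply no value.

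**The case against.** The plan does not contradict itself. It consistently defines the clean period as freedom from the outcome, Section 9.1.1 says only that such a period may be required, and nothing obliges a covariate list to match it. Section 9.9 also admits miscoding and incomplete comorbidity history, though only in general terms. All of that is fair. It does not change what the rule does when it is followed.

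Several stronger readings are tempting, and the documents do not support them:

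- **That anyone with one of the 63 codes becomes a case when the code changes.** The new code must be one of the 25, in a qualifying setting and within the window or follow-up. A move between two of the 63 never counts, and Section 9.7.1.1 drops people with events in both SCRI windows.
- **That all 63 codes mark established glomerulonephritis.** Only 22 say so. Others are unspecified proteinuria or hematuria (N06.9, N02.9), other hereditary nephropathy (N07) or glomerular disorders in other diseases (N08). A later specific code in such a person may be new disease, so a blanket N00-N08 exclusion could remove true cases.
- **That the cohort is confounded because the kidney term pools too much.** The propensity score also holds immunocompromised status, immunomodulators, oral corticosteroids and utilization counts. Section 9.7.2.1 allows an outcome-specific model. These may partly balance prevalent patients but do not remove them. Residual imbalance is possible, not shown.
- **That only a few people would be affected.** The documents give no basis for any number.

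Review of estimates approaching the signal threshold is allowed and softens the consequence of dilution, but it is optional.

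**Conclusion.** The point holds. As written, the clean period lets through prior-year disease carried under 63 glomerular codes, 22 of which name glomerulonephritis, and counts it as incident once one of the 25 outcome codes first appears in a qualifying setting and period. The code counts are exact.

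The size of the bias is unknown. The SCRI figures above rest on two assumptions: recodings make up 10% to 50% of all counted events, and they fall evenly in both windows. A much smaller share would make the effect negligible. For the cohort, no direction of remaining bias can be claimed.

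This affects one of 20 safety outcomes, but the change is cheap and should be made. The outcome list lacks the mark of FDA CBER BEST origin. Table 2 notes that neither interval for this outcome could be taken from the literature, so the definition is the sponsor's own to adjust.

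**What to change.** Add one line to Table 2 or Section 9.2.2.2. For the glomerulonephritis analysis in both phases, Days -365 to 0 (inpatient or outpatient) must be free of any N00, N01, N03, N04 or N05 code and of any N02, N06 or N07 code labelled glomerulonephritis, including the '.A' codes. Keep the 25 codes as the event definition.

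Of the codes in the two lists, this screens 50 (N00, N01, N03-N05) + 15 (five each in N02, N06 and N07) + 7 ('.A') = 72 instead of 25. The remaining 88 − 72 = 16 are the less specific N02, N06 and N07 codes and N08. Screen these too in a sensitivity analysis with the full N00-N08 exclusion.

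Cost: the people excluded leave this one analysis, and under Section 9.7.2.1 so do their matched comparators. At the 1:10 ratio that section gives as an example, one excluded vaccinee could take ten comparators along. A few true new cases may also be lost. Outcome-specific exclusions are applied after matching, so the propensity score model and the master cohort do not change.
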